Using their database and a pre-screening tool, HIAS will identify potential participants who meet the following criteria: women, at least 18 years of age, at risk of GBV or ever experienced GBV, have a migratory permit (for migrants and refugees), are Colombian or Venezuelan, have been residing in Colombia for at least six months, and have an entrepreneur profile registered with HIAS. Individuals with the targeted characteristics will then be further screened for study eligibility using the Self-Reliance Index (SRI). First launched in 2020, the Self-Reliance Index (SRI) is the first-ever global tool for measuring the progress of refugee households toward self-reliance (Seff, Leeson, and Stark, 2021). Eligible participants must receive a score between 2 and 3.5 on the tool to be included in the study. This range of scores aims to capture women who are vulnerable, but who are in a stable enough situation to develop an income generating activity (meaning that they are not unhoused or in need of urgent humanitarian assistance), while still in need of financial support, training and GBV assistance. If a participant's score on the SRI falls outside of the specified range, they will be ineligible for further inclusion, thanked for their time, and removed from the study. Participants whose score falls within the specified range will be included in the study and further baseline data will be collected including information on mental health, empowerment, and safety.

Subject Recruitment, enrolment and sample size

HIAS will use their database and the pre-screening tool to identify potentially eligible participants for the study. They will aim to identify approximately 90-100 potentially eligible women through

the pre-screening tool. Official enrollment, consenting, and formal assessment of eligibility will be carried out by the research team. Data collectors will obtain written consent from previously pre-screened women prior to administering the SRI. After administering the SRI, data collectors will immediately administer the remaining survey questionnaire modules for participants whose SRI scores fall within the eligible range of 2 to 3.5. Women whose scores fall outside of the 2-3.5 range will be thanked for their time and not assigned to an evaluation arm.

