Participants may feel compelled to consent to the study in spite of the above-mentioned informed consent procedures. Potential power differentials between the participants and data collectors may result in inadvertent coercion to participate in the study. The research team will carefully analyze the context-specific factors that may result in participant coercion and discuss strategies for ensuring genuine informed consent. Some of the measures that may be used include:

- Build on existing staff experience with informed consent procedures in other projects.

- Intensive staff training on the importance of informed consent and procedures to minimize potential coercion. Such procedures may include careful explanation and repetition of the nature of voluntary consent (e.g., participation in the study will not affect access to services; participants are free to refuse to answer any questions or to withdraw from the study at any time). Participants will also be given time to consider their decision.
- Multiple opportunities for participants to ask questions throughout the informed consent process and subsequent data collection. Researchers will be trained to respond to frequently asked questions or concerns that participants may raise. Close collaboration with HIAS staff to avoid recruiting participants who may be unable to provide assent voluntarily due to mental health or cognitive disability.

Data Collection

Participant data will be collected at three time points: baseline (when participants are first enrolled in the study), eight months post-baseline (upon program completion), and three months following endline data collection (eleven months after baseline). Data collectors will be hired and trained by Los Andes and the RSRI team members using a combination of online learning modules and in-person training, which will cover the study tools, evaluation protocol, humanitarian principles and its current practice, safeguarding policies, Psychological First Aid (PFA) gender and GBV, and research ethics and best practice.

Study Outcome Measures and Ascertainment

Self-reliance:

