The following describes the procedure designed in conjunction with all strategic areas of HIAS, with the aim of providing clarity on the comprehensive case management and referral pathways we regularly implement as an organization to ensure the protection of our beneficiaries and provide an immediate response to their needs.

HIAS has a robust network of services for the population, as well as referral and counter-referral pathways with other humanitarian organizations and institutional entities to ensure the protection of participants.

Chart 1. Procedure for case management and referrals within the SRI-PRM research project

Stage 1. Preparation for a situation or need

The HIAS Colombia team prepares to address the needs of IDPs through actions that promote the appropriate approach and management of cases based on a rights-based, gender-based, and age-based approach, which complies with humanitarian principles and prevents actions that cause harm.

In summary, the following strategies will be implemented:

- HIAS staff will be trained to comply with strict confidentiality standards for case management.
- Clear referral pathways to HIAS services are available, and, if required, external referral pathways will be activated with partner organizations and entities.
- HIAS services are implemented in a coordinated and complementary manner. Constant communication channels will be established between the Economic Inclusion area and other HIAS areas to avoid duplication of care, prevent re-victimization of participants, and facilitate access to services.

Additionally, at HIAS, we work closely with government institutions, partner organizations in the territories, the private sector, and refugee communities, promoting local integration and access to rights and services.

Stage 2. Identification of situations or needs

When needs or situations arise that affect the psychosocial well-being of our IDPs and/or threaten their continued participation in the program, the HIAS Colombia team will be able to respond to the case by activating the corresponding route, depending on whether it is a GBV or MHPSS case.

Likewise, the following strategies will be developed:

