- IE Officers and Research Assistants who will be present at the training and data collection spaces will be trained to address any type of situation or need by providing crisis support and Psychological First Aid to individuals experiencing emotional distress, family conflicts, domestic violence, and suicidal thoughts.
- IE Officers will then inform the IDPs about the services available at HIAS (GBV Case Management, Individual Psychosocial Care, and Legal Protection) and will ask each individual if they would like to be referred to any of these services.

Stage 3. Recording the Situation or Need

When participants express a need to be assisted by HIAS professionals, the needs and/or situation assessment process is activated.

Likewise, the following actions will be carried out:

- Internal referral forms will be used to describe the identified situation, the level of risk identified, the priority range under which the case should be addressed, and whether the participant's consent is obtained.
- Once the PDI's consent is obtained, the IE Officer will carry out the referral process to the GBV Case Manager or the MHPSS Officer, using the internal case referral forms provided by the MHPSS and GBV department.
- The MHPSS and GBV services at HIAS Colombia conduct risk and needs assessments to determine the support participants require, as well as to negotiate access to additional services with partner organizations. Should external referrals arise, the GBV Case Manager or the MHPSS Officer will be responsible for making them and following up on them.
- The Economic Inclusion Officer will follow up on referrals and will be in contact with the MHPSS Officer or GBV Manager in charge of providing care to the beneficiary.

HIAS Colombia has developed a matrix of physical and psychosocial risks associated with the implementation of the gender-responsive entrepreneurship school program, and has also implemented risk mitigation actions for each situation.

Stage 4. Response to the situation that occurred or need encountered

4. Respuesta a la situación ocurrida o necesidad encontrada

- Cualquier situación de riesgo o necesidad será canalizada por el Oficial de Inclusión Económica, quien deberá remitir a los Oficiales SMAPS y Gestor de casos VBG según se requiera.
- Los asistentes de investigación deberán comunicar de manera inmediata al Oficial de Inclusión Económica sobre la situación y este deberá activar la ruta interna de remisión correspondiente.

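### PHQ-9 is a primary outcome in the SAP, but the visible plan does not have its score totalled for safety purposes or linked to referral

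*Protocol*

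**What the plan says.** **The measure.** SAP section 2 lists PHQ-9, range 0 to 27, as one of three primary outcomes, with higher scores meaning worse depressive symptoms. SAP section 5.1 models change in each outcome, so PHQ-9 must be given at least twice. The protocol's eligibility section says that "further baseline data will be collected including information on mental health, empowerment, and safety", and its recruitment section says that "data collectors will immediately administer the remaining survey questionnaire modules" once a woman's SRI score is in range. The protocol's outcome measures section covers self-reliance, resilience, empowerment and gender-based violence. It lists no depression scale.

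**The referral route (protocol, Safety and Adverse Events).**
- Stage 2 opens with "When needs or situations arise that affect the psychosocial well-being of our IDPs and/or threaten their continued participation in the program". Staff at training and data collection sessions are trained in "providing crisis support and Psychological First Aid to individuals experiencing emotional distress, family conflicts, domestic violence, and suicidal thoughts", and Economic Inclusion Officers then ask each woman whether she wants a referral.
- Stage 3 says: "When participants express a need to be assisted by HIAS professionals, the needs and/or situation assessment process is activated". Referral follows her consent.
- Stage 4, in Spanish, says: "Cualquier situación de riesgo o necesidad será canalizada por el Oficial de Inclusión Económica". It adds: "Los asistentes de investigación deberán comunicar de manera inmediata al Oficial de Inclusión Económica sobre la situación". The officer must then activate the internal route.
- The MHPSS referral criteria include recurrence of distress, its severity (mild, moderate or severe), interference with functioning and weak coping. They name no instrument and no cut-off.
- The one numeric scale threshold in the procedure is a 3-point Warwick Scale gain. It is a condition for closing a case, not for opening one.

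**Training.** The protocol's Data Collection section says data collectors' training includes "safeguarding policies, Psychological First Aid (PFA) gender and GBV, and research ethics and best practice".

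**The concern.** The trial takes a structured measure of depressive severity from women enrolled because they have experienced, or are at risk of, gender-based violence. The protocol's own background says that depression and anxiety are expected in this population and are more pronounced in survivors. The referral criteria ask about severity, and the survey measures a form of it, yet no visible step carries the measurement to the people who apply the criteria.

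At stake is a woman whose answers add up to a moderate or high total but whom the interviewer does not recognise as distressed and who asks for nothing. If the plan is followed as written, her interview can end with the score untotalled and no referral offered.

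**Working it through.** The plan states no figure on this point, so there is none to reproduce. The check is a reading of each way into the referral route, followed by short arithmetic on the score range.

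**Step 1. What starts each part of the route?**

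| Part of the route | What starts it | Uses the PHQ-9 result? |
|---|---|---|
| Stage 2 | A need or situation arises; staff respond to distress or suicidal thoughts | No |
| Stage 3 | The participant expresses a need | No |
| Stage 4 | A situation of risk or need, reported at once by research assistants | No |
| MHPSS criteria | Officer identifies frequency, severity and functioning; MHPSS officer assesses from the referral form | No |
| Case closure | Includes a 3-point Warwick gain | Not an entry point |

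Every entry depends on a member of staff recognising something or on the woman voicing it. PHQ-9 appears in the SAP's outcome list and nowhere else in the visible text.

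**Step 2. Who would recognise it?** Data collectors give the survey and have Psychological First Aid training. Stages 2 and 4 speak of research assistants. The documents do not say whether these are the same people. I take them to be; if they are not, the Stage 4 duty may not bind the interviewer and the gap is wider.

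**Step 3. Why would a flag need both an item rule and a total?** Input: range 0 to 27 (SAP section 2). Assumption: standard content, meaning nine items scored 0 to 3, one of them on self-harm. The documents do not reproduce the items; the range is consistent with this, since 27 / 3 = 9.
- Self-harm item 0, the other eight at the maximum of 3: 8 × 3 = 24, and 24 / 27 = 88.9%.
- Self-harm item 0, the other eight at 2, so that no answer is at the maximum: 8 × 2 = 16, and 16 / 27 = 59.3%.
- Self-harm item alone positive: total 1 to 3, that is 1 / 27 = 3.7% to 3 / 27 = 11.1%.

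Recognising suicidal thoughts alone therefore leaves totals up to 24 to judgement, and any cut-off above 3 can miss a woman whose only positive answer is on self-harm. These figures describe the scale. They do not count women missed.

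**The case against.** The strongest reply is that the plan already handles the serious cases. If PHQ-9 is given by interview, as the protocol's wording on administration suggests, a woman who totals 24 with the self-harm item at 0 has told a trained interviewer of eight symptoms at their maximum. That fits emotional distress under Stage 2 and a situation of risk or need under Stage 4. A spoken self-harm answer fits even more clearly. The MHPSS criteria also give staff a frame of frequency, severity and functioning. This stands, and it moves the gap away from the extreme scores towards totals that no single answer makes obvious.

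A reader might infer that the trial has no plan for suicidal thoughts, or that high scorers fall outside every criterion. The documents support neither. Suicidal thoughts are named in Stage 2, and descriptive referral criteria exist, though staff must still apply them without an instrument or cut-off.

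Three further points have weight:
- **Unseen material.** Chart 1 (the referral procedure), the risk matrix, the questionnaire and other HIAS protocols are not visible. A trigger could sit in any of them, so absence is shown for the visible text only.
- **Outside knowledge.** The self-harm item is assumed from the standard instrument.
- **Trade-offs.** Passing a survey answer to the programme provider is a safeguarding choice with costs, and Stage 3 puts consent before referral.

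None of this supplies the missing step of totalling the score and acting on it.

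**Conclusion.** The point holds in a narrow form. The protocol does not list a measure that the SAP treats as primary, and in the visible text no one is told to total it and no referral criterion refers to it. Moderate-to-high scorers who are not recognised as distressed may be offered no referral. Spoken self-harm answers and obvious distress are probably covered already.

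The size is unknown: the documents give no rate of high scores and none is assumed here. The conclusion rests on standard PHQ-9 content, on data collectors being the research assistants of Stages 2 and 4, and on the unseen HIAS material holding no such rule.

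This is a cheap improvement of optional to modest priority, with medium confidence. A reader might go further and infer that women at risk are being left without care; the documents do not show that. The case for a flag is that it relies less on recognition alone and uses an officer, a route and a reporting duty that already exist.

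**What to change.** 1. List PHQ-9 and its time points in the protocol's outcome measures section.
2. Add a rule to Stage 2 for every remaining survey round at which PHQ-9 is given, in both arms. The survey form totals the score. It flags any answer above 0 on the self-harm item, or a total at or above a cut-off that the MHPSS team fixes beforehand. A flag counts as a Stage 4 situation: the interviewer notifies the Economic Inclusion Officer before the interview closes, and the officer offers referral the same day.
3. State in the consent wording that such answers are passed to HIAS. Keep referral itself subject to the woman's consent under Stage 3, and record acceptance or refusal on the internal referral form.
4. Report flags, offers and referrals by arm.

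If Chart 1, the risk matrix or another HIAS protocol already contains such a rule, cite it in Stage 2 in place of item 2.

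**Timing.** The SAP, dated April 2024, describes randomization in the past tense, so baseline is probably over. The documents do not show which rounds remain. Item 1 is worth doing regardless.

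**Cost.** A short amendment, a total and a flag in the form (or nine answers added by hand), brief retraining, and an officer reachable during survey sessions. MHPSS staff would receive more referrals, in unknown number. Some women may under-report once told that answers are passed on. Survey-triggered care in both arms could itself shift PHQ-9, which is the reason for reporting by arm. The sample size and the analysis models do not change.

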Ø There is evidence of a reduction in the occurrence of psychosocial indicators (subjective distress)

Ø The person shows less irritability and/or aggressive behavior

Ø The person shows less distress when speaking and recounting something related to their painful experience

Ø The person returns to enjoying activities they had usually avoided

Ø The person feels more motivated to talk with others

Ø The person becomes active in daily activities

Ø The person seeks more help

Ø The person reports fewer somatic symptoms

Ø The person reports having more tools to cope with their problems

Ø The person shows an increase in their emotional well-being of at least 3 points on the Warwick Scale

Once the MHPSS Officer verifies that there has been a notable improvement in the IDP's psychosocial well-being, they are responsible for finalizing the individual intervention and proceeding to close the case.

GBV SERVICE REFERRALS

Among the services offered by the GBV area, GBV Case Management provides comprehensive support to women, girls, adolescents, survivors, or members of the LGBTQI+ community who are experiencing any type of violence or are at risk of being subjected to violence due to their gender or factors associated with it.

GBV case management is carried out in three modalities: cross-border, emergency, and comprehensive. Case management includes a process for profiling individuals, assessing their GBV risk level, designing an action plan based on specific GBV needs, outlining commitments and objectives for case management. It also includes making the respective internal and

external referrals to services that mitigate the identified needs, conducting case follow-up, and ultimately closing the case. If the IE Officer identifies any risk or situation of violence among participants participating in the EGSE, they may initiate a referral route to the GBV Case Manager, who will receive, assess, and provide management for the specific case. The GBV Officer will provide support to the Case Manager and provide technical guidance while providing care. The GBV Officer will follow the global protocols developed by HIAS for the management of gender-based violence cases, as well as guidelines based on international standards.

Criteria for Referrals to GBV Case Management

In accordance with the GBV Case Management Action Plan, and specifically the needs of the GBV person, referrals are made to the services they require, which we offer both internally and externally.

The criteria defined for referrals to this service are:

- Ø Risk of rights violations due to gender
- Ø Being abused and/or discriminated against (physically, verbally, financially, and psychologically) and/or humiliated because of their gender
- Ø Being a member of the LGBTQ+ community and being subjected to violence (physically, verbally, financially, and psychologically) or perceiving themselves at risk of being subjected to violence due to their gender.

Reasons for Closing GBV Cases

To proceed with the closure of GBV cases from the case management service, the following conditions must be met:

- Ø Loss of contact with the survivor for more than one month
- Ø Withdrawal from the process by the survivor
- Ø Compliance with objectives within the framework of rights and services management
- Ø Compliance with the maximum of 6 follow-up sessions that can be provided.

Compliance with these conditions is validated by the GBV Case Manager, who also provides the support and follow-up required by the PDI. The GBV Officer provides supervision and technical support for the appropriate handling of all GBV cases.

Data analysis

Quantitative data analysis

Preliminary and descriptive analyses will include: one-way frequency distributions of each survey item and item composite scores, including measures of central tendency (e.g. mean) and variability (e.g. standard deviation) for continuous, approximately normally distributed composite scores. Cronbach's alpha of 0.6 and above will be used as a threshold cut-off to determine the reliability of the composite scores.

We will also model the variation in participants' responses across time. We will test and compute effect sizes for the following hypotheses:

- Directly following program implementation, women who participate in the intervention will exhibit greater improvement in outcomes, compared with women who do not participate in the intervention.
- Three months following the completion of program implementation, women who participate in the intervention will exhibit greater improvement in outcomes, compared with women who do not participate in the intervention.

9. Molenberghs, G., & Verbeke, G. (2000). Inference for the random effects. *Linear Mixed Models for Longitudinal Data*, 77-92.

Trabajo de campo

Protection of human subjects

Are you going to work with human subjects?

- Yes
- No
- Otro:

Are you going to work with any of these communities?

- LGBTI communities
- Prisoners
- Victims of the armed conflict
- Clinical patients
- Students
- Black communities
- I will not be working with communities
- Other: GBV survivors and women at risk En caso de trabajar con otra comunidad, por favor mencione cuál.
- Other: Socioeconomically vulnerable women.

Conflict of Interest

We encourage you to declare any conflict of interest you believe may affect the project in question. For more information about conflicts of interest, please visit our page.

No competing interests need be disclosed for any of the researchers involved in the study.

Ethical Considerations

In a maximum of 500 words, outline the ethical considerations that will be taken into account in the implementation of the project, clearly identifying at what points in the project's development ethical dilemmas are anticipated and explaining how you plan to avoid or resolve them in your research. Ethical dilemmas may relate to: data collection, handling, and archiving; conflicts of interest; fabrication, falsification, and plagiarism; research with human subjects; animal research; the project's social responsibility; the project's environmental impact; and issues of authorship and funding, among others. If you do not answer this question, the committee will not consider your project.

According to Resolution number 008430 of 1993 of the Colombian Ministry of Health and Social Protection, this is "research without risk", which includes: "studies that employ retrospective documentary research techniques and methods and those in which no intervention or intentional modification of the biological, physiological, psychological or social variables of the individuals participating in the study is carried out, including: review of medical records, interviews, questionnaires and others in which no sensitive aspects of their behaviour are identified or dealt with".

The study is expected to carry minimal risk of loss of confidentiality associated with participation in group discussions, which will be minimized by data confidentiality measures and by using verbal informed consent procedures. Individuals have the option to not participate, or if they choose to participate, to decline to answer any question that they do not feel comfortable answering, or to choose to end their participation in the study at any time. We do not anticipate any psychological risk that may result from study participants. All measures will be taken to minimize the risk related to the contracting and spreading COVID-19 among any of the researchers or study participants, following the guidelines of the Ministry of Health and the University. All focus group and feedback discussions will be conducted in-person.

Additional detailed information on the consenting process and handling of adverse events and referrals can be found in the protocol above.
